MI-SI. Participants who are randomized to the experimental treatment will receive one or two sessions of MI-SI on the unit (see manual in Appendix). The overarching goal of MI-SI is to shift motivation away from suicide and towards living and recovery. MI-SI consists of three phases: 1) exploring the presenting problem, 2) building the motivation to live, and 3) strengthening the commitment to living. In phase 1, clinicians and patients explore patients' presenting problem and their thoughts about suicide, which amplifies their reasons for living. In

phase 2, clinicians help patients explore their reasons for living including a detailed exploration of their beliefs and values to enhance their motivation to live. In phase 3, clinicians instill hope and strengthen patients' confidence that they can establish a life that is worth living by helping them develop a concrete plan. The plan is written out on a worksheet that is provided to the patient at the end of the session. Transitioning between phases is dependent on the willingness of participants to follow the clinicians' direction, as requiring participants to transition through the phases before they are ready to do so may reduce the impact of MI-SI. For example, requiring patients who are not ready to develop concrete plans to do so has been found to undermine their commitment to follow-through with their plans. 

In session 1, clinicians will attempt to proceed through all three phases. In session 2, clinicians will summarize session one and use patients' response to the summary to decide which phase to return to. If patients are in phase 3, clinicians' will help them refine and reinforce their plan. If they are undecided about mental health or substance abuse treatment, clinicians will return to phases 1 or 2 and explore reasons against engaging in treatment, build the motivation to engage in it, and strengthen their commitment to do so. Veterans in the MI-SI condition will also complete one telephone booster MI-SI session (30-50 mins.) within one-month (weeks 3-6) after discharge. Telephone contact within one month after discharge is a component of treatments that have been found to reduce risk for suicidal behavior and will be used to increase the dosage of MI-SI.  Participants will be provided a handout with the scheduled telephone follow-up and therapist contact information. Telephone sessions will consist of an abbreviated MI-SI interview following the strategy of session 2. For telephone sessions, phase 3 will include a review of their mental health and substance abuse treatment and explore alternative or additional treatments if they are called for. All MI-SI sessions will also be recorded for coding.

TAU. All patients that are admitted to the acute psychiatric unit receive standard inpatient treatment that includes medication management, case management, meals and a bed, and milieu therapy consisting of creative and social activities (e.g., crafts, video games, karaoke). Families of Veterans may also receive education concerning the Veteran's problems to create a supportive home environment. Suicidal patients receive additional services. VA mental health clinicians are required to complete a Safety Plan with all suicidal Veterans, and each VAMC has hired a Suicide Prevention Coordinator (SPC) to oversee the care of high-risk patients. The Syracuse VAMC also hired Case Managers to help meet essential living needs of suicidal Veterans. SPCs and Case Managers work collaboratively to help suicidal patients transition from inpatient to outpatient treatment. Chart reviews will provide a detailed description of the components of TAU that each participant receives so that suicide-specific TAU can be described in detail. Suicide-related TAU will be controlled for in analyses if differences are observed between conditions.

**In-Hospital Follow-ups.** These assessments will be conducted 2-3 days and 3-5 days after the baseline assessment, during the course of hospitalization. If patients are discharged during this time, only the first follow-up will be obtained. Participants will be asked to complete a "modified" SI that assesses suicidal ideation over the past 48 hours to assess recent change , Contemplation Ladders and the PDM. When it is time to conduct the in-hospital follow-up assessment, a researcher on the unit will call a researcher at the CoE who will conduct the assessment by telephone. This will ensure that outcome assessments are conducted by researchers who are blind to condition.

**Post-Discharge Follow-ups.** Follow-up assessments will be conducted at 1, 3, and 6 months via telephone. A telephone follow-up will enable us to expand the catchment area and assess

participants who are hospitalized or in residential treatment and unable to return to the medical center. Procedures will include mailing participants the assessment measures to ease administration. There is precedence for this strategy, as the telephone administered SSI was the primary outcome for the PROSPECT trial, supporting use of the method.  In addition to the SSI, we will also use all risk-factors measures that are used at baseline including the PHQ-9, PCL-C, BAI, AUDIT, DAST-10, SUF, InDUC, ISI, C-SSRS, Contemplation Ladders, HCCQ, TSRQ, PCQ, PDM as well as the exploratory outcome measure the TSR-6 (Table 3). The window for each assessment will open at the midpoint between the previous assessment and the current assessment, and close at the midpoint between the current assessment and the following assessment (e.g., open two weeks before month 1 and close at the end of month 2, the midpoint between 1 and 3 month assessments), and close 3 months after the 6-month follow-up.

Comprehensive tracking procedures will be implemented to follow-up with participants. Because we found no methodological papers on following-up with Veterans our follow-up procedures were informed by the substance abuse research methodology literature as individuals with substance use disorders are notoriously difficult to follow. 89-91 Procedures were revised after the pilot study. Tracking procedures will include: 1) careful hiring, training, and supervision of study personnel; 2) establishing rapport and clarifying procedures with participants; 3) obtaining detailed identifying information and locator data; 4) obtaining contact information for friends and family members who may assist in locating the participant; 5) remunerating participants for their time and effort; 6) making it easy for participants to contact staff personnel and leave messages; 7) providing assistance to participants when they request it; 8) maintaining flexibility and ease in scheduling and keeping appointments; 9) designing a follow-up assessment battery that is not burdensome: 10) providing a handout with scheduled follow-up assessments and researchers contact information; 11) contacting participants in advance of appointments; 12) making repeated and varied contact attempts; 13) updating contact information regularly using contacts and medical records; 14) and asking for consent to contact VA and non-VA treatment facilities that they may receive care from. The follow-up assessment will be used to measure outcomes and risk factors for suicidal behavior.

At each follow-up we will also inquire about use of the Safety Plan that was completed on the inpatient unit. We will ask 1) if participants remembered doing the Safety Plan, 2) where they keep their Safety Plan, 3) if they used it while having suicidal thoughts, and 4) how they used it.

Chart Reviews. Research assistants will review participants' charts at two points during the study. The baseline chart review will take place after the baseline interview. Research assistants will cull treatment data from VA medical records using a protocol that we have used in a previous study. Center staff has received 8 hours of training in the protocol and achieved inter-rater reliability as part of the previous study. The protocol emphasizes suicidality, service engagement in the past year, services received during the visit prior to hospitalization, and risk factors for suicide such as depression and substance use disorders. Follow-up chart reviews will occur in concordance with the 6-month follow-up assessment. The protocol will be an abbreviated version of baseline protocol, with the time period limited to the 6 months following discharge. The chart review will also be used to assess use of VA suicide prevention services including the Safety Plan, SPCs, High-risk List, and case managers so that we can describe TAU components that participants receive. Center research assistants already trained in the chart review protocol that will be used. If additional assistants need training, we will use the existing training protocol, which consists of 8 hours of training in the protocol and reviewing practice charts.

**Research Assistant Training and Supervision.** Research assistants will conduct all assessments and receive detailed training and supervision to ensure standardization.

Initial Training. The PI will provide initial training in the detailed interview-based measures. In this initial training, all staff will also receive training in the safety procedures (described in the patient safety section). The interviews contain three measures that require extensive training and supervision to achieve consistency of administration and scoring: SSI, TSR, and C-SSRS. Training for these measures will make use of lectures to learn about the measures and role-plays to reach proficiency. The PI will observe research assistants' first two research interviews to ensure that they are using the instruments appropriately and provide corrective feedback. If indicated, interviews will be observed until proficiency is reached. Training and supervision for each measure are included below. All administrations will be recorded and random samples will be independently coded for reliability. Researchers will use digital recorders on the unit, and earbuds that plug into the recorders for telephone assessments.

SSI training: [name] has received training from the developers of the SSI, used it extensively, and trained the PI in its administration and scoring. The PI will provide two hours of training for the research assistants.

TSR training: The PI has used the TSR in both pilot studies that were conducted with high-risk Veterans. Research assistants will receive two hours of training for the measure.

C-SSRS training: The PI has received training in the administration and scoring of the C-SSRS from [name], the developer of the measure. He will provide two hours of training in the C-SSRS for the research assistants.

Weekly Supervision. The PI will provide weekly supervision for the research assistants and lead a monthly half-day meeting in Canandaigua. The agenda will include a review of participant flow including recruitment, scheduling, and retention of subjects; issues pertaining to administration, scoring, entering, and storing interview protocols; subject safety issues; consensus meetings for SSI ratings; consensus meetings for chart reviews; discussion of adverse events; and on a quarterly basis, reviewing the quality of data gathered. Research assistants will also review one another's interview packets for completeness and errors at these meetings.

**MI-SI Training and Supervision.** MI-SI will be delivered by masters and doctorate-level research clinicians who will have received specialized training and supervision.

MI-SI Training. Training will consist of sixteen hours. It will consist of 8 hours of training in general MI followed by eight hours of MI-SI training. Training modalities include listening to power-point presentations, selected readings from the MI text  and the MI-SI manual (included in Appendix), MI exercises, and listening to and discussing recorded examples of MI-SI. The PI will observe the first two interviews to ensure that therapists meet MITI fidelity criteria and provide corrective feedback. Additional training activities will be scheduled as necessary.

MI-SI Supervision. An RCT evaluating methods for training MI clinicians found that ongoing coaching and/or feedback is needed to maintain proficiency in MI.  The PI will provide weekly supervision for MI-SI clinicians, focusing on promoting the fidelity of MI-SI by discussing

difficult cases, listening to and discussing recorded MI-SI interviews, and reviewing MI materials and publications.

**Interview Coding and Training.** MI-SI sessions will be recorded and coded for fidelity using the MITI,  which requires specialized training.

MITI Coding and Training. The MITI is a behavioral coding system that is used to code 20-minute samples of tape for adherence to MI principles (e.g. empathy, autonomy support) and use of specific MI techniques (e.g. reflections, open questions). Summary values from coded interviews will be used to assess fidelity,  and provide material for supervisory sessions. A random selection of interviews will be double-coded and inter-rater reliability will be computed using inter-class correlation coefficients. 

The PI will provide MITI training to the research assistants who are coding the MI-SI therapy sessions. The protocol that will be used is identical the one use by [name]., an MI Training expert who trained coders for Project MATCH,  and trained the PI. Training will consist of eight hours and include reviewing the MITI coding scale, coding MI interviews and comparing the codes to "gold standard" codes available on the MI website,  and coding recordings of MI-SI interviews. Coders will be considered reliable when they achieve reliabilities of good or better (ICC > .60) on 80% of MITI codes. 

MI-SCOPE Coding and Training. The Sequential Code for Observing Process Exchanges (SCOPE),  will be adapted for use with suicidal clients. SCOPE is a coding scheme developed to examine sequential therapeutic interactions between clinicians and clients to study the psychotherapy process and its relation to treatment outcome.  It includes the codes used for the MITI, and additional codes for clinicians (e.g., confrontation, emphasize control, feedback), and clients (e.g., follow, ask, commitment). We will adapt the MI-SCOPE by adding codes for living and suicide talk, and other suicide-related statements. Interviews are transcribed, and both transcripts and audio recordings are used for coding. A random selection of interviews will be double-coded and inter-rater reliability will be computed using inter-class correlation coefficients. 

The PI will also provide MI-SCOPE training to the research assistants who are coding the therapy sessions. The MI-SCOPE protocol is identical to that used by the developers of MI-SCOPE.  Because the MI-SCOPE is more intensive, training will consist of sixteen hours and include reviewing the MI-SCOPE coding scale, coding MI-SI interviews and comparing the codes to "gold standard" codes that the PI derives. Coders will be considered reliable when they achieve reliabilities of good or better (ICC > .60) on 80% of MITI codes. 

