**CPRS Notes.** After the informed consent process is completed, researchers will enter a Study Initiation Note into the participants' digital medical record. To ensure that mental health staff is aware of patients' participation, the attending psychiatrist and nurse manager of the unit will be added as a signees. They will also be added to MI-SI session noted which will document whether the individual exhibited suicidal ideation, plan, or intent during the session.

Participant Procedures. The study will consist of three phases. Phase 1, the assessment phase (15 min.), will be conducted on day 2 or 3 of hospitalization to confirm eligibility. Eligible participants will immediately complete the baseline assessment of risk factors and outcome variables (50 min.). Phase 2, the treatment phase, will occur between day 2 or 3 and discharge. Participants will be randomized to MI-SI plus TAU or to TAU alone. The MI-SI plus TAU condition will include one or two sessions of MI-SI (50 mins. each) in addition to TAU. Sessions will be held on consecutive days and recorded using a digital audio recorder, which will be coded for clinician fidelity. Phase 3, the follow-up phase, will take place after discharge. Participants in the MI-SI plus TAU condition will complete 1 booster MI-SI telephone session within 1 month of discharge (30-50 min.). All participants will be contacted by telephone to complete follow-up assessments (50 min.) at 1, 3, and 6 months to measure outcome variables and risk factors. Research assistants who are blind to condition will complete follow-up assessments.

Table 3: Complete List of Measures

			Time of Assessment			
Domain	Measure	Purpose	Screen	Baseline	*Follow-ups	**Follow- ups after discharge
Demographics	UAB	Screen				
Veteran Status	UAB	Screen				
Psychotic Disorders	MINI	Screen				
Manic Episode	MINI	Screen				
Cognitive Deficits	MMSE	Screen				
ТВІ	TBI-ID	Screen				
Suicidal Ideation (SI)	SSI	Outcome				
Depression	PHQ-9	Risk Factor				
PTSD	PCL-C	Risk Factor		$\sqrt{}$		
Anxiety	BAI	Risk Factor		$\sqrt{}$		$\sqrt{}$
Alcohol Use	AUDIT	Risk Factor		$\sqrt{}$		$\sqrt{}$
Drug Use	DAST-10	Risk Factor		$\sqrt{}$		
Substance Use	SUF	Risk Factor		$\sqrt{}$		$\checkmark$
Frequency						
Substance Problems	InDUC	Risk Factor		V		V
Insomnia	ISI	Risk Factor		V		$\sqrt{}$
Anger	LHA	Risk Factor		V		
Suicidal Behavior	C-CSSRS	Risk Factor		V		V
Contemplation Ladders	CL	Risk Factor		√	$\sqrt{}$	$\sqrt{}$
Treatment Engagement	TSR	Outcome		√		$\sqrt{}$

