- 7. Drug Use Consequences (15 items): The Inventory of Drug Use Consequences (INDUC)  $^{67}$  is the gold-standard self-report assessment of substance-related consequences in the past 90 days. It has been used with Veterans.  $^{68}$
- 8. Insomnia (7 items): The Insomnia Severity Index (ISI) is a widely used, reliable and valid self-report instrument of sleep difficulty. 
- 9. Anger (5 items): The Lifetime History of Aggression Questionnaire (LHAQ) is a brief, valid, and reliable measure of aggression .
- 10. Treatment Engagement (26 items): Treatment engagement will be measured using the Alcohol and Drug Services, Medication, Medical Services, and Psychological Services sections of the Treatment Services Review (TSR-6) which have been shown to be both reliable and valid. 71 The TSR-6 will be used at baseline and the 1, 3 and 6 month follow-ups to inquire about use of these services. The baseline assessment will be used to compare engagement in psychological and alcohol and drug service use between groups to assess whether it needs to be accounted for in the analyses. Engagement in psychological and alcohol and drug services will also be assessed at each follow-up assessment and used as an exploratory outcome. Treatment engagement will be treated as a dichotomous outcome, and will be defined according to the Substance Abuse and Mental Health Services Administration (SAHMSA) Washington's Circle standards, 72 which have been adopted by VA. 73 For residential patients and inpatients, treatment engagement is defined as attending two outpatient visits in the 30-days after discharge. In Veterans with substance use disorders, this measure of treatment engagement has been found to be associated with treatment outcome 74 and hospitalization in those with a suicide attempt history. 75 In Veterans discharged from psychiatric hospitalization, completing two outpatient sessions in at least two of the six months after discharge has also been found to be associated with suicide. 1
- 11. Suicidal Behavior (18 items): The Colombia Suicide Severity Rating Scale (C-SSRS)  will be used to assess history of suicidal behavior at baseline and at follow-up assessment. It has been mandated for use in medication trials by the FDA. 

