Primary Analysis 1: An over-dispersion Poisson generalized linear mixed model (GLMM) with maximum likelihood estimation will be used to examine the effect of MI-SI on the severity of SI at 1, 3, and 6 months follow-up. GLMM was chosen because random effects are added to the model to account for repeated measures within subjects. An over-dispersion Poisson GLMM will be used because the SSI is bounded at zero and had a standard deviation larger than the mean at follow-up in our pilot data, indicating over-dispersion. If data do not meet the assumptions of a Poisson distribution, we will use a negative binomial or zero-inflated negative binomial. The benefit of using maximum likelihood estimation is that it yields unbiased estimates in the presence of missing data, if data are missing at random. Because participants may receive one or two sessions of MI-SI, and the change pattern may not be linear over time, we will test sessions of MI-SI, time of assessment, and their interaction in follow-up analyses. As an added measure of clinical significance, we will report the number of participants in each group who fall below the two-point cut-off.

Because the presence of any suicidal behavior (i.e., attempted suicide, interrupted attempts, preparatory behavior) is an important outcome, we will use a mixed effects general logistic model to examine the effect size of MI-SI on the incidence of suicidal behavior as measured by the C-SSRS over follow-up assessments.

Exploratory Hypothesis 1: Participants who receive MI-SI plus TAU will engage in more treatment over follow-up than participants who receive TAU alone.

Exploratory Analysis 1: Multivariable logistic regression will be used to examine the effect of MI-SI on treatment engagement. The Hosmer-Lemeshow statistic will be used to evaluate model fit, and odds ratios with 95% confidence intervals will be derived using the method of maximum likelihood.  Because participants may receive one or two sessions of MI-SI, we will conduct a sensitivity analysis examining the number of MI-SI sessions as a predictor of treatment engagement. Because this is an underpowered exploratory analysis, we will also conduct secondary analyses using other definitions of treatment engagement such as number of sessions attended.

We will also examine the impact of the intervention on use of the Safety Plan coping strategies. To test treatment differences, we will use a multivariable logistic regression.

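### Nothing keeps the MI-SI arm's telephone booster out of the treatment-engagement count, so it can add a contact in one arm only to the outcome and mediator of Exploratory Hypotheses 1 and 2

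*Combined protocol and SAP*

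**What the plan says.** Item 10 of the Baseline Assessment (General Procedures) makes TSR-6 service use the source: "Engagement in psychological and alcohol and drug services will also be assessed at each follow-up assessment and used as an exploratory outcome". The outcome is dichotomous, and for patients leaving inpatient care "treatment engagement is defined as attending two outpatient visits in the 30-days after discharge". Exploratory Analysis 1 in the Analytical Plan adds a count: "we will also conduct secondary analyses using other definitions of treatment engagement such as number of sessions attended". Exploratory Analysis 2 uses engagement from the TSR as an observed mediator between randomised arm and SI.

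The booster is described twice. Participant Procedures has: "Participants in the MI-SI plus TAU condition will complete 1 booster MI-SI telephone session within 1 month of discharge". The MI-SI description under Treatment Conditions has: "Veterans in the MI-SI condition will also complete one telephone booster MI-SI session (30-50 mins.) within one-month (weeks 3-6) after discharge". It is given by masters- or doctorate-level research clinicians, and its third phase reviews the participant's mental health and substance abuse treatment.

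The section on blind outcome assessments keeps follow-up interviewers unaware of arm. No section includes the booster in the engagement variables, and none excludes it.

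**The concern.** A 30 to 50 minute conversation with a study clinician about suicidal thoughts and treatment is something a participant could reasonably report when asked about psychological services. Only one arm receives it. If it is reported and counted, delivery of the intervention becomes part of the outcome meant to measure its effect on other care. One call supplies half of the two-visit threshold and a full unit of the session count.

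The blind interviewer does not know who had a booster and so cannot knowingly leave it out. Study records will show who had one and when, but not whether that person's TSR-6 answer included it. Subtracting one from every MI-SI count would over-correct for those who left it out. The rule therefore has to be in place before the interviews.

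At stake are Exploratory Hypothesis 1 and the arm-to-engagement path of Exploratory Hypothesis 2. The second is to be judged on effect sizes, so a shifted path would feed directly into what is reported.

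**Working it through.** **The plan's own figures.** None is given for engagement. The only power figures concern the SSI, and they reproduce: variance factor (1 + 2×0.70)/3 + 1 − 2×0.50 = 0.80; effective SD 8.4×√0.80 = 7.51; with 45 per arm, one-sided power .935, .811 and .598 for 5, 4 and 3 points, against the stated .94, .81 and .60. Engagement does not enter that calculation.

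**Session count.** If booster completion is r, the MI-SI mean rises by r sessions. Taking r from 70% (assumed as a lower bound from Pilot Study #1, where that share completed both MI-SI sessions) to 100% gives 0.7 to 1.0, whether or not the call falls within 30 days.

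**Two-visit outcome.** With no true effect on outside care, the false gap is q × b × r:
- q = share with exactly one outside visit in 30 days, since only they are pushed over the threshold;
- b = share of boosters falling within 30 days;
- r = share completed. All completed calls are taken as reported and accepted as visits.

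*b.* Weeks 3-6, spread evenly: days 21-42 give 10/22 = 45%; days 15-42 give 16/28 = 57%. If every call falls within 30 days, b = 100%.

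*q.* The documents give no 30-day visit distribution. The only anchor is Pilot Study #1: 7 of 11 had four or more sessions (exact 95% interval 31% to 89%). I take the period as the pilot's 60-day follow-up, which is inferred. Two assumed shapes:
- Poisson: P(N ≥ 4) = 7/11 gives a mean of 4.38 in 60 days, 2.19 in 30. P(≥2) = .643, P(≥1) = .888, so q = .245.
- Geometric (overdispersed): ρ = (7/11)^¼ = .893; 60-day mean .893/.107 ≈ 8.36, 30-day mean 4.18; 30-day ρ = 4.18/5.18 = .807. P(≥2) = .807² = .651; q = .807 × .193 = .156.

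| False gap | Geometric | Poisson |
|---|---|---|
| b = 45%, r = 70% | .156×.45×.70 = 4.9 points | .245×.45×.70 = 7.7 points |
| b = 57%, r = 100% | .156×.57 = 8.9 points | .245×.57 = 14.0 points |
| b = 100%, r = 100% | 15.6 points | 24.5 points |
| booster not counted | 0 | 0 |

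Weeks 3-6 timing therefore gives about 5 to 14 points. If every booster is inside 30 days, the upper case is about 25. Letting q run from 10% to 30% without a distribution widens the whole range to 3 points (.10×.45×.70) through 30 points (.30×1×1).

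**What this does to a test.** For 45 per arm and a one-sided two-proportion test, the rejection rate is Φ[(d − z·SE₀)/SE₁], with SE₀ from the pooled rate and SE₁ from the two separate rates.
- d = .049 (.651 to .700): SE₀ = .0987, SE₁ = .0986. At .05, (.049 − 1.645×.0987)/.0986 = −1.15, so .13. At .01, (.049 − 2.326×.0987)/.0986 = −1.83, so .03.
- d = .140 (.643 to .783): SE₀ = .0954, SE₁ = .0942. At .05, (.140 − 1.645×.0954)/.0942 = −0.18, so .43. At .01, (.140 − 2.326×.0954)/.0942 = −0.87, so .19.

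With the booster excluded, these return to .05 and .01.

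**The case against.** The documents never say that the booster counts. The binary definition speaks of outpatient visits, and the booster is a telephone research session. The plan also appears to regard MI-SI as distinct from treatment: the booster reviews the participant's other care, and Exploratory Analysis 1 uses the number of MI-SI sessions as a predictor of engagement. Whether the TSR-6 items would pick up a study call cannot be checked from the documents. All of this stands, so a reader who infers that engagement is inflated by design goes further than the text allows. But none of it is an exclusion rule, and none of it tells a participant what to report.

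A reader might also infer that blinding makes the problem unsolvable. It does not: an instruction given identically to both arms needs no knowledge of arm. Recordings carry an ID, session type and date, and the CPRS Notes section says of the unit's attending psychiatrist and nurse manager, "They will also be added to MI-SI session noted which will document whether the individual exhibited suicidal ideation". That does not specifically say the post-discharge call is noted. These records can support a check, but they cannot reveal what a self-reported count contained.

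The size is open to challenge too. The pilot rate comes from 11 people who all received MI-SI, so it is not a TAU rate, and the visit distribution is assumed. Hence a range, with 25 points as the upper case and not the expected value.

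Finally, the affected hypotheses are exploratory, declared unpowered, and held to .01 if reported with the main trial. That limits the consequence but does not remove the bias, particularly where conclusions rest on effect sizes.

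**Conclusion.** The gap is real and worth closing, but it shows possible inflation, not established inflation. If the booster is reported and counted, it adds up to one session per MI-SI participant. It also adds roughly 5 to 14 points to two-visit engagement under weeks 3-6 timing and 70% to 100% completion. About 25 points is the upper case, needing every call completed, reported, accepted as a visit and inside 30 days with Poisson visits. The effect is 0 if the call is not reported or not accepted. The inpatient MI-SI sessions precede discharge and cannot enter the 30-day definition.

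It might be inferred that Exploratory Hypothesis 2 could be confirmed by the extra contact alone. The documents do not support that: mediation also needs an association between engagement and SI, which a miscounted call does not itself create. What it can distort is the arm-to-engagement path, and so the size of any indirect effect. The primary SSI analysis and its power are unaffected.

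**What to change.** - Keep the TSR-6 as the source. Before it is administered, give every participant in both arms the same instruction not to count any study contact, whether an assessment or a study session. This preserves the blind.
- State in Baseline Assessment item 10 and in Exploratory Analyses 1 and 2 that study-delivered MI-SI contacts do not count in the binary outcome, the number of sessions or the mediator.
- Use study session records and the planned 6-month chart review as a check or sensitivity analysis. Replacing the TSR-6 with chart-derived visits is not needed; the follow-up review is an abbreviated one, and the plan does not say that dated visits are extracted.
- Reconcile the two descriptions of booster timing in Participant Procedures and under Treatment Conditions, since the share of calls inside 30 days depends on them.

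The cost is one added interview instruction, a few sentences in the plan and slight extra data handling.
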